Study Protocol and Statistical Analysis Plan

Study title: Standard vs Long IV Catheter Long-Term IV Survival Comparison

NCT number: NCT03655106

Document date: Mar 19, 2019

Catheter length and IV Survival: Standard vs Long IV Catheter Long-Term IV Survival Comparison

Background/Scientific Rationale:

Patients with poor intravenous (IV) access present a daily challenge to emergency department (ED) practitioners. Placement of an ultrasound (US)-guided peripheral IV catheter in this patient population is a viable and safe option. Successful cannulation with US-guided IV occurs in more than 90% of cases compared with 25-35% with traditional IV placement in patients with difficult vascular access.¹⁻³ Once cannulated, however, the failure rate of IV catheters placed under ultrasound guidance is concerning compared with traditional blind IV placement. Overall failure rates after successful IV cannulation for US-guided IVs is 45-56% when compared to traditional IV placement which is 19-25%.⁴⁻⁸

Nearly all hospitalized patients need IV access for treatment. If access is lost, patients may experience treatment delays, dissatisfaction from repeat needle-sticks, and health complications if the patient's condition becomes critical. IV failure can result in a number of negative outcomes including interrupted medical therapy; painful phlebitis and reinsertions; increased hospital length of stay, morbidity and mortality from infections and/or skin necrosis from caustic medication infiltration; utilization of invasive procedures such as peripherally inserted central catheters (PICC) and central lines; and wasted medical/nursing time.⁹

Ultrasound-guided IVs are often the last recourse for IV access before resorting to more invasive procedures in patients with difficult access. Because failure rate is high, it is important to approach insertions methodically to improve survival rates. There are several characteristics of US-guided IV placement that have shown to increase catheter survival. Anatomic variations shown to increase US-guided IV longevity include placing catheters more distally in the arms and in veins that are shallow.¹⁰ Another study determined that using a catheter over a guide-wire improves catheter longevity.⁷ However, these catheters are costly, are not readily available within most EDs, and may require sterile technique.

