A variable that may alter the survival of US-guided IVs that has not been studied extensively is the length of catheter that resides in the vein. Currently the general accepted rule is that an "adequate" amount of the catheter should be in the vein to avoid failure of the catheter.¹¹⁻¹⁴ However, this recommendation is only anecdotal and there has been no study to verify or quantify it. Our preliminary data focused on defining this relationship. In our study, **100% of catheters failed** in which less than 30% of the catheter was placed within the vein and **no failures** in those IVs in which at least 65% of the catheter was in the vein. All catheters in this analysis were commonly available 4.78 cm IVs. A key challenge for inserters is that achieving this quantity of catheter length in vein is impractical at the recommended angle of insertion when considering deeper target vessels. For many institutions, including ours, the 4.78 option is the longest stocked IV catheter and catheter survival is negatively impacted.

Central Hypothesis/Objectives:

We hypothesize that using an Ultra Long IV (6.35 cm) catheter increases the likelihood of ensuring a higher quantity of the catheter in the vessel lumen and leads to improved catheter longevity.

Primary Objective: Compare the IV survival between the Ultra Long IV (UL IV) (6.35 cm/20G) and the Standard Long IV (SL IV) (4.78 cm/20G) placed under US-guidance.

Function is defined as ability of catheter to flush 5 mL without resistance with or without blood sampling.

Secondary/Tertiary Objective(s):

Determine catheter survival based on vein depth.

Determine optimal cutoff length of catheter in vein for best survival profile.

Determine catheter survival based on angle of insertion.

Quantify specific etiologies related to premature catheter failure comparing UL IV to the SL IV.

Quantify overall costs associated with placement of the UL IV compared to the SL IV.

Determine overall success of placement UL IV versus SL IV.

Determine first-stick success UL IV compared to SLIV.

Determine number of attempts and time to insertion comparing UL IV to SL IV.

Safety Endpoint(s):

Compare phlebitis and thrombosis complication rates between the Ultra Long IV and the Standard Long IV.

[figure not shown]
Compare infection rates for all catheters.

Study Design:

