If the catheter was identified to have any signs or symptoms of complications during follow-up assessment the date and time of observation of the complication will be documented in the data collection tool and the primary team will be notified of the complication. If the catheter was removed prior to the follow-up assessment then the IV removal time and the reason for removal will be obtained through chart review. For all catheters removed due to a complication, re-insertion attempt data will be tracked through the medical record in the nursing section for venous lines and need for reinsertion of the IV or escalation to a midline, PICC, or CVC will be noted. If the patient is discharged prior to the time of follow-up assessment then the time of discharge will be documented and the IV will be presumed functional until time of discharge unless otherwise noted in the chart.

The medication administration record will be queried for all medications given through each catheter. Vesicants/irritants that are generally given via central line or considered caustic to the vessel will be noted in both groups. Number of doses will be recorded. See Appendix D for full list of non-neoplastic vesicants/irritants.

Additional data gathered by research staff on follow-up evaluation includes: dwell time in days/hours, hospital length of stay, and number of peripheral IVs or rescue catheters for duration of stay.

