Appendix E represents the data collection documentation tool for all medications.

SVT and DVT rates will be calculated based on upper extremity proven diagnosis of SVT and/or DVT in symptomatic cases. Researchers will review all study subject records in EPIC and screen for all upper extremity venous Doppler examinations. Radiology interpretations will be reviewed for findings of consistent with thrombus. This review will occur thirty days post patient discharge.

Infection rate will be tracked using confirmed blood stream infection data from epidemiology. These are cases in which line sepsis or bacteremia is confirmed by positive blood cultures.

Cost difference between approaches will be tracked. Equipment costs and personnel costs will be tracked. Number and type of IV catheters inserted/attempted will be extracted from the medical record. Supply costs will be estimated based on number of IVs attempted. Median time to successful catheter placement will serve as a baseline for estimating time needed for future reinsertions. Time will be assigned a monetary value. We will also track the number of patients from each group that require a PICC or CVC as a rescue catheter.

Sample Size and Power Analysis:

For this randomly allocated two-groups experiment, the primary outcome is catheter survival. Sample size calculation is based on primary outcome: composite or all cause premature removal due to complication of the IV catheter. Based on literatures and a new published article immediately prior to study period, we estimate sample size using the median survival time 30 hours for the 4.78 cm standard IV option. 91 subjects per group for a total sample size of 182 subjects is the minimum recommendation assuming a 10% dropout rate. This calculation

achieves power of 80% to detect a hazard ratio of 0.63 or less for line failure of the 6.35 cm ultra long IV based on log-rank test.

Statistical Analysis:

Characteristics of enrolled and eligible patients will be summarized between two arms using means [standard deviations] and medians [interquartile ranges] compared by t-tests or Wilcoxon tests for continuous variables and frequencies (percentages) compared by chi-squared tests or Fisher's exact tests for categorical variables.

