Survival analysis methods (Kaplan-Meier curves, the log-rank test for continuous failure times or logistic model for discrete failure times) will be used for analyzing times to IV failure with non-failure times treated as censored. Proportions of SVT, DVT and catheter infection rates will be reported separately for each arm. Nonparametric summaries and a Wilcoxon Rank sum test will be used for the cost data. To test the effect of catheter variables on survival, we will further use Cox proportional hazard regression models for time-to-event outcomes and logistic regression models for binary outcomes. P-values of less than 0.05 will be considered statistically significant. Analysis will be conducted using SAS 9.4.

Study Site:

William Beaumont Hospital, Royal Oak (RO) campus is the proposed site for the investigation. It is a 1,100 bed major academic and referral center with Level 1 adult trauma and Level 2 pediatric trauma status. A major teaching facility, Beaumont, Royal Oak has 55 residency and fellowship programs with 454 residents and fellows. Beaumont is the exclusive clinical partner for the Oakland University William Beaumont School of Medicine. The Beaumont Research Institute was established more than 30 year ago at Royal Oak and offers research support services to clinical investigators.

The Royal Oak (RO) Emergency Center (EC) has the resources available to complete this project. This site is a tertiary care, level I trauma center with an annual ED census greater than 130,000 visits. I collaborated with nursing leadership in 2015 and implemented an ancillary staff-training program for placing US-guided IVs. Nearly forty ancillary staff members are certified in this procedure. Further, weekly logs of IVs placed under US-guidance show that an average of 10 US-guided IVs are placed daily. The RO EC has 130,000 annual visits of which many patients have difficult access. We also have 11 portable US machines with high frequency linear transducers that are ideal for vascular imaging.

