Appendix C: Functionality and Complications

Day	Functional 1: draw 2: flush 3: infusing 4: failed	Removal Time	Reason for Remov al	Venous Doppler 1: + for dvt 2: + for svt 3: + for dvt/svt 4: - for both 5: none	Lab confirmed infection Y/N	Discharge <24 hrs from insertion	Replacement Access in the case of failure 1: Midline 2: PICC 3: PIV 4: US PIV 5: CVC	Research staff initials
1								
2								
3								
4								
5								
6								
7								
8								
9								
10								
11								
12								
13								
14								
15								
16								
17								
18								
19								
20								
21								
22								
23								
24								
25								
26								
27								
28								
29								
30								

Reasons for Removal: (1) Completion of therapy; (2) infiltration; (3) infection; (4) dislodgement; (5) leaking; (6) pain; (7) other; (8) unknown

Post processing data

Angle of Insertion (°)	Length in vein (cm)	% Length in Vein

Signature/Date: _____

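### Kaplan-Meier is the only absolute summary of failure over time that is named, and it censors catheters that end without failing; its complement would overstate the share that actually fail, by an amount that depends on rates the documents do not give.

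*Combined protocol and SAP*

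**What the plan says.** - **Event.** Sample Size and Power Analysis defines the primary outcome as "composite or all cause premature removal due to complication of the IV catheter".
- **Methods.** Statistical Analysis names "Survival analysis methods (Kaplan-Meier curves, the log-rank test for continuous failure times or logistic model for discrete failure times"), which "will be used for analyzing times to IV failure with non-failure times treated as censored". It adds that "we will further use Cox proportional hazard regression models for time-to-event outcomes and logistic regression models for binary outcomes". Simple proportions are planned for SVT, DVT and infection. No cumulative incidence function or other competing-risk method appears.
- **Ends without failure.** The Appendix C code list begins "Reasons for Removal: (1) Completion of therapy; (2) infiltration; (3) infection; (4) dislodgement", so code 1 is a non-failure end. Under Follow-up Assessment, for a patient discharged before the next check, "the IV will be presumed functional until time of discharge unless otherwise noted in the chart". Death is not mentioned, but a death with a working catheter would also be a non-failure time.
- **Early discharges.** Study Design removes from the survival analysis patients discharged with a working catheter of under 24 hours' duration.
- **Rates the trial argues from.** Background: "Overall failure rates after successful IV cannulation for US-guided IVs is 45-56" per cent. Preliminary Data: 29 failures among 86 catheters (33.7%), with checks to 72 h.
- **Etiology objective.** "Quantify specific etiologies related to premature catheter failure comparing UL IV to the SL IV". No method is assigned to it.

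**The concern.** Ordinary censoring means that the event could still happen after observation stops. A catheter removed because therapy is finished, or taken out at discharge, cannot fail later. If these ends are censored, Kaplan-Meier passes their future on to the catheters still in place, and its complement answers a hypothetical question: how many would fail if none were removed electively and nobody went home?

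That is a legitimate description of device durability. It is not the share of catheters that fail in practice, which is the quantity a clinician needs for absolute benefit and the one the pilot's 29/86 describes. The plan does not say which of the two its curves represent, and it offers no second summary. The risk is that failure percentages read off the curves are taken as patient experience, are set beside the motivating rates, or yield an absolute difference between arms that is too large.

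The etiology objective is exposed too. If Kaplan-Meier were applied cause by cause, the other failure causes would also be censored and the cause-specific figures could add to more than 100%.

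**Working it through.** The plan states no figure on this point, so there is none to reproduce. The check asks how far the complement of Kaplan-Meier (1-KM) departs from cumulative incidence (CIF) under the plan's own inputs.

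**Inputs from the documents.** Control median 30 h and hazard ratio 0.63 (Sample Size and Power Analysis); overall failure 45-56% (Background).

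**Assumptions.** Constant hazards; the 45-56% read as the crude share of standard-arm catheters that ever fail; the same competing hazard in both arms. The documents give no rate of completion, discharge or death.

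**Formulas.** Failure hazard f = ln2/30 = 0.0231 per h (standard) and 0.63 × 0.0231 = 0.01456 per h (ultra-long). Competing hazard c = 0.0231 × (1-p)/p, where p is the share that ever fail in the standard arm.

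- 1-KM(t) = 1 - exp(-f·t)
- CIF(t) = f/(f+c) × [1 - exp(-(f+c)·t)]

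**Case A: nobody excluded.** Worked example, standard arm, p = 0.50 (c = 0.0231), 72 h: 1-KM = 1 - exp(-1.664) = 81.1%; CIF = 0.5 × [1 - exp(-3.327)] = 48.2%; gap 32.8 points.

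| Arm, time | 1-KM | CIF, p = 0.45 | CIF, p = 0.56 | Gap (points) |
|---|---|---|---|---|
| Standard, 48 h | 67.0% | 41.2% | 48.3% | 25.8 to 18.7 |
| Standard, 72 h | 81.1% | 43.9% | 53.1% | 37.2 to 27.9 |
| Ultra-long, 48 h | 50.3% | 29.7% | 35.2% | 20.6 to 15.0 |
| Ultra-long, 72 h | 64.9% | 32.5% | 40.3% | 32.5 to 24.7 |

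At p = 0.50 the difference between arms at 48 h is 67.0 - 50.3 = 16.7 points by Kaplan-Meier and 44.6 - 32.3 = 12.3 by CIF. At 72 h it is 16.1 against 12.1.

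**Case B: every non-failure end before 24 h excluded.** This is the widest reading of the Study Design exclusion. At p = 0.50 in the standard arm, the excluded share is 0.5 × [1 - exp(-0.0462 × 24)] = 33.5%, leaving 66.5%. By 24 h another 33.5% of all catheters have failed, so survival in the retained set is 1 - 0.335/0.665 = 0.496. At 72 h, 1-KM = 1 - 0.496 × exp(-0.0231 × 48) = 83.6% and CIF = 0.482/0.665 = 72.5%, a gap of 11.1 points. Over p = 0.45 to 0.56 the gap is 5.1 to 3.8 points at 48 h and 12.4 to 9.6 at 72 h.

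**Case C: half of those early ends excluded.** The exclusion names only discharged patients, so an inpatient whose therapy ended before 24 h stays in and is censored. If half of early non-failure ends are discharges, simulation gives 13-18 points at 48 h and 20-28 at 72 h.

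**Case D: the retained set itself has 45-56% failure, with no non-failure end before 24 h.** The gap is 12-22 points at 48 h and 25-36 at 72 h.

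**Case E: slower non-failure ends, nobody excluded.** With c = ln2/72, the standard-arm gap is 11.1 points at 48 h and 17.2 at 72 h. With c = ln2/168 it is 5.1 and 8.2.

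**Hypothesis test.** In 4,000 simulated trials per setting with equal failure hazards and this censoring, the log-rank test rejected in 4.8% (p = 0.45) and 5.3% (p = 0.56).

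**The case against.** The strongest reply is that the primary objective is to compare how long two devices work. For that, censoring at elective removal is a standard choice, and Kaplan-Meier is valid for survival while in use if the censoring is independent. The plan never says that it will report 1-KM as the share of patients who fail, and it lists no failure proportions at 24, 48 or 72 h. This stands. The defect is an unlabelled estimand and a missing summary, not a wrong primary analysis.

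Four stronger readings are tempting, and the documents do not support them.

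- *Only Kaplan-Meier is planned.* Log-rank, discrete-time logistic, Cox and logistic models are also named. The narrower statement holds: none of these is set up to give the absolute share failed by a stated time.
- *The overstatement is a flat 20 to 35 points.* That needs an assumed competing rate and ignores the early-discharge exclusion. The 45-56% and the 30 h median come from cited sources that need not describe the same population, and Background does not say how its rates were calculated.
- *The primary test is biased.* It compares failure hazards, for which this censoring is appropriate.
- *The cost results are distorted.* They rest on counts of catheters, placement time and rescue lines, compared by a Wilcoxon test. Dwell time is recorded directly.

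A further objection is that adding CIF alone would not recover the share of all placed catheters that fail. This is correct. In Case B, CIF in the retained set is 72.5%, against 48.2% among all catheters, so the exclusion matters as much as the method. The fix has to deal with both.

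**Conclusion.** The point holds as one about absolute reporting. Non-failure ends are censored, no cumulative incidence is planned, and 1-KM would overstate the share of catheters that fail in both arms.

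Across the cases worked, the standard-arm gap runs from about 4 to 26 points at 48 h and about 8 to 37 points at 72 h. The upper end needs 45-56% overall failure with nobody excluded. The lower end needs either slow elective removal or exclusion of every early non-failure end. All of it rests on constant hazards and an assumed competing rate, so no single figure should be quoted as the size.

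The log-rank and Cox comparison stands, and Kaplan-Meier stands as survival while the catheter stays in use. The plan should be changed because the change is cheap and the absolute results would otherwise invite misreading.

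**What to change.** In Statistical Analysis:

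1. Keep Kaplan-Meier, the log-rank test and the Cox model. Label the Kaplan-Meier curves as catheter survival while still in use.
2. Add the cumulative incidence of failure by arm (Aalen-Johansen) at 24, 48 and 72 h. Treat completion of therapy, discharge with a functional catheter and death as competing events, and give a risk difference with 95% CI.
3. For this summary, keep patients discharged with a functional catheter before 24 h in the denominator as competing events, instead of applying the Study Design exclusion.
4. Report failure etiologies as cumulative incidences, with the other causes also competing.
5. Use these figures for any statement of failure rate or absolute benefit.

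Cost: plan wording and a few lines in SAS 9.4 (PROC LIFETEST with EVENTCODE). Removal reason, removal time and discharge time are already to be collected, and Appendix C flags discharge within 24 hours. Death has no code of its own there and would need one. The downside is a second set of curves to present, and an absolute failure rate and benefit that look smaller.

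### The safety objective is to compare the two catheters, but the plan specifies only separate per-arm proportions, with no between-arm estimate or interval and no summary of phlebitis

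*Combined protocol and SAP*

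**What the plan says.** Two safety endpoints are listed under Safety Endpoint(s): "Compare phlebitis and thrombosis complication rates between the Ultra Long IV and the Standard Long IV" and "Compare infection rates for all catheters". The second does not name the arms, but in a two-arm trial a between-arm comparison is its natural reading.

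The Statistical Analysis section has one sentence on these endpoints: "Proportions of SVT, DVT and catheter infection rates will be reported separately for each arm".

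The Follow-up Assessment section says how events are found. For thrombosis: "SVT and DVT rates will be calculated based on upper extremity proven diagnosis of SVT and/or DVT in symptomatic cases", by screening all upper-extremity venous Dopplers in the record, and "This review will occur thirty days post patient discharge". For infection: "Infection rate will be tracked using confirmed blood stream infection data from epidemiology". The same section lists "dwell time in days/hours, hospital length of stay" among the follow-up data, so exposure time is recorded.

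**The concern.** An objective to compare needs an estimate of the difference and its uncertainty. The analysis text gives neither, and nothing else in the section supplies them. The t, Wilcoxon, chi-squared and Fisher tests are tied to patient characteristics. The Cox and logistic models are tied to the effect of catheter variables on survival. Cost data get a named between-arm test; safety does not. Phlebitis is named in the objective but is absent from the analysis sentence, and it is not a coded removal reason in Appendix C.

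The design adds a difficulty of interpretation. The hypothesis is that ultra-long catheters last longer. If complications accrue with time in place, a per-patient proportion combines risk per day with the longer dwell that is the intended benefit. The Potential Impact section expects longer dwell to reduce thrombosis and infection. Two separate proportions give that claim no stated test.

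**Working it through.** **The plan's own figure.** The safety sentence states none, so there is nothing to reproduce. The check uses the planning values under Sample Size and Power Analysis: control median 30 h, hazard ratio 0.63, 91 per arm.

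**1. Expected dwell.** Assume exponential survival. The hazards are λ_S = ln 2/30 = 0.02310 per h and λ_U = 0.63 × 0.02310 = 0.01456 per h. Mean dwell capped at τ is (1 − exp(−λτ))/λ.

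| Cap τ | Standard (h) | Ultra-long (h) | Ratio |
|---|---|---|---|
| 48 h | 29.0 | 34.5 | 1.19 |
| 72 h | 35.1 | 44.6 | 1.27 |
| 120 h | 40.6 | 56.7 | 1.40 |
| 168 h | 42.4 | 62.7 | 1.48 |
| none | 43.3 | 68.7 | 1.59 |

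The caps are assumptions. The plan follows catheters for as long as the patient is in hospital and gives no fixed length.

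**2. Effect on proportions.** Assume the same constant hazard h in both arms, with events only while the study catheter is in place. The proportion is h/(h + λ) × (1 − exp(−(h + λ)τ)). The documents give no event rates, so take h from 0.25% to 3% per day. The ultra-long to standard ratio then runs from 1.19 to 1.58. At 1% per day (standard v ultra-long):

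| Cap τ | Proportion | Events per 91 | Per 1,000 catheter-days |
|---|---|---|---|
| 48 h | 1.20% v 1.43% | 1.09 v 1.30 | 9.9 v 9.9 |
| 120 h | 1.67% v 2.32% | 1.52 v 2.11 | 9.9 v 9.8 |
| 30 days | 1.77% v 2.78% | 1.61 v 2.53 | 9.8 v 9.7 |

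The expected gap is 0.2 to 0.9 events per 91 patients.

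**3. Replacement lines.** Take a 120 h (5-day) stay and 1% per day. Study-catheter exposure is 1.69 v 2.36 days. Suppose replacement lines at the same daily risk cover a fraction f of the remaining days. Exposure is then d + f(5 − d), and risk is 1 − exp(−0.01 × exposure).

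- f = 0: 1.68% v 2.34%, ratio 1.39.
- f = 0.5: 3.35 v 3.68 days, 3.29% v 3.61%, ratio 1.10.
- f = 1: 5 v 5 days, ratio 1.00.

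**4. What a catheter-day rate would do without attribution.** Suppose cumulative risk per patient is equal in the two arms, and all events are divided by study-catheter dwell. The rate ratio is then the inverse of the exposure ratio: 1/1.27 = 0.79 at a 72 h cap and 1/1.59 = 0.63 with no cap. That would be a spurious advantage for the ultra-long arm.

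**5. Precision.** With 0 of 91 events, the one-sided 95% upper limit is 1 − 0.05^(1/91) = 3.2%. For 0 v k events with 91 per arm, the two-sided Fisher p-value is 2 × C(91,k)/C(182,k). This gives 0.059 for k = 5 and 0.029 for k = 6, so at least 0 v 6 is needed for p < 0.05. Starting from one event, 1 v 8 is needed.

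**The case against.** The best defence is that the planned summary is sound as far as it goes. A per-patient proportion by randomised arm is a valid measure of cumulative risk. If counts and denominators are printed, a reader can work out a difference and an exact interval. Complications that lead to removal also enter the primary time-to-failure analysis, which accounts for time at risk, and a secondary objective compares causes of failure between arms. All of this stands. It limits the point to SVT, DVT, infection and phlebitis as safety endpoints, and it means the proportions should be kept. It does not supply the comparison that the protocol says it will make.

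A reader might go further and infer that the ultra-long arm is bound to look less safe, by 27% to 59% (the ratios at a 72 h cap and with no cap). The documents do not support that:

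- They give no event rates and do not say that risk is constant over dwell. The Potential Impact section expects complications to fall.
- Thrombosis comes from all upper-extremity Dopplers, reviewed 30 days after discharge, and infection from epidemiology data. No rule ties either to the study catheter. Replacement lines in the arm that fails earlier could bring the ratio to 1.00.
- The upper end needs unlimited dwell, whereas catheter follow-up ends at discharge and completion of therapy is a listed removal reason. A 48 h cap gives 1.19, below the lower end of that range.
- At an assumed 1% per day the expected gap is less than one event per 91 patients, so chance would outweigh it.

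**Conclusion.** The gap is real and minor. The safety endpoints call for a comparison; the analysis text provides separate proportions with no between-arm estimate or interval, and nothing for phlebitis. This follows from the wording alone and needs no numerical assumption.

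The exposure concern is conditional. It needs exponential survival at the planning values, a constant and equal daily risk, and events confined to study-catheter dwell. Under those assumptions the ratio of proportions is about 1.2 to 1.6, shrinking towards 1.0 as replacement lines contribute events. It justifies a supplementary rate, not replacement of the proportions or a prediction about which arm will look worse. Nor should a reader infer that dividing by recorded dwell time is enough by itself: with unattributed events it could mislead in the opposite direction.

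**What to change.** In the Statistical Analysis section:

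1. Keep the per-patient proportions and state their denominators.
2. Add the between-arm risk difference with an exact 95% CI for SVT, DVT and infection. Do the same for phlebitis if it is captured, which needs a definition and a code on the Appendix C form.
3. State that safety will be interpreted from the intervals, not from p-values.
4. As a supplement, report events per 1,000 catheter-days by arm with a rate ratio and exact 95% CI. Count only events attributed to the study catheter by a rule fixed in advance (for example, same arm or vein and within a stated window), so that the numerator matches the dwell-time denominator.

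The cost is small. Dwell and removal times, Doppler results and confirmed infections are already collected, and Appendix B records the side of the successful site. The added work is a few lines of analysis and a modest effort to attribute events. The drawback is that the intervals will be wide, which is a fair picture of what 91 patients per arm can show.
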